Patients with MS, regardless of disease course, who fulfil all inclusion criteria and none of the exclusion criteria, will be randomized in a 1:1:1 ratio to exergames or adaptive COGNI-TRAcK or sham COGNI-TRAcK. This study includes two periods (training period and follow-up period) and three visits (see the **FIGURE** below):

- on Week 0, at study enrolment/randomization (baseline visit);
- on Week 8 (+/- 5 days), i.e. after the end of the 8-week training period (Week 8 visit);
- on Week 16 (+/-5 days), i.e. at study termination after the 8-week post-training follow-up period (Week 16 visit).

Eligibility criteria

For inclusion:

- (i) age between 18 and 55 years (inclusive);
- (ii) cognitive impairment, defined as failure in the SDMT, defined as a corrected score less than 38, i.e. below the 5th percentile of normative value [31];
- (iii) Expanded Disability Status Scale (EDSS) score between 2.0 and 5.5 [32];
- (iv) ability to stand upright for at least 180 seconds without any support;
- (v) ability to understand and comply with study requirements;
- (vi) ability to provide a valid informed consent before any study procedure.

For exclusion:

- (i) relapse in the previous 6 months;
- (ii) initiation of disease-modifying or symptomatic treatments or physiotherapy programme in the 3 months prior to study entry;
- (iii) any medication/physiotherapy changes occurring over the previous 3 months;
- (iv) significant visual impairment, defined as a Visual System scoring more than 2 at the Kurtzke Functional Systems Score [32];
- (v) clinically relevant depression, defined as Beck Depression Inventory-II (BDI-II) score equal or more than 14 [33];
- (vi) overt dementia, defined as an adjusted Mini Mental State Examination (MMSE) score equal or less than 24 [34];
- (vii) history of epilepsy or seizures;
- (viii) any medical condition, including musculoskeletal disorders that can interfere with the study conduction.

Randomization procedure

Randomization codes will be computer-generated in blocks of six to ensure an approximate 1:1:1 balance between the three arms. Randomization codes will be assigned at baseline visit sequentially within each center as patients become eligible for randomization by an independent organization not involved in study conduction. Once a block is exhausted, the next available block will be allocated to a center upon the next randomization.

Blinding

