The blinding is ensured by using single-blind technique. A two-operator (treating and assessing) model is used to assist with study masking. The treating operator at each site is **not blind** to intervention arm and he/she is responsible for evaluating patient eligibility, for explaining how to use the devices and for recording and managing AEs. The assessing operator is an independent neuropsychologist or physiotherapist who is **blind** to intervention arm and he/she is exclusively responsible for on-study assessments.

Study discontinuation and drop-out

Patients who are screened for enrolment, but not randomized (e.g. because they do not fulfill eligibility criteria or do not provide a valid informed consent) will be considered as **screening failure** and their data will be not analyzed.

Patients are free to discontinue any intervention at any time, without prejudice to further treatment or care. A patient who decides to discontinue whatever training protocol will be considered as **drop-out** and he/she will always be asked about the reason(s) for discontinuation and the presence of any AE. Premature discontinuation of whatever training protocol does no impact on the patient's participation in the study, since the patient will always be asked to continue attending the subsequent study visit to ensure complete data for an intention-to-treat analysis.

If the patient does not agree to continue in-person study visits, he/she will be considered as **lost to follow-up** and a modified follow-up must be arranged via telephone contact to ensure at least the collection of safety information.

STUDY PLAN AND TIMING OF PROCEDURES

Visit	Week 0 Screening Randomization Baseline	Week 8 (+/- 5 days) Immediate post-training	Week 16 (+/- 5 days) Study Termination
Signed informed consent	X		
Eligibility criteria	X		
Demographic and clinical data collection (CRF)	X		
EDSS score	X		
BDI	X		
MMSE	X		
Randomization & study code assignment	X		
CRIQ	X		
HLAQ	X		
TCI	X		
BICAMS (including SDMT, CVLT2, BMVT-R)	X	X	X
SCWT	X	X	X
2MWT (single-task & dual-task)	X	X	X
Static posturography (single-task & dual-task)	X	X	X
MSIS-29	X	X	X
MFIS	X	X	X
WPAI:MS	X	X	X
Physical activity data collection (actigraph)		X	X
Check of adherence to intervention protocol		X	
Check of AEs		X	X
Device for intervention	Dispense	Return	
Patient diary	Dispense	Return	
Logbook	Dispense	Check	Return
Actigraph	Dispense	Check	Return

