Phone contact are planned every two weeks to encourage patients to perform the training and to remind them to complete the patient diary and logbook throughout the study period.

Recruitment and randomization (Baseline visit)

Consenting patients are assessed to ensure they are eligible for the study, i.e. meet all inclusion criteria and none of the exclusion criteria. Patients who are not eligible must not be randomized in the study.

The following procedures will occur during the baseline visit:

- Obtain signed informed consent before any study-related procedure;
- Confirmation of patient eligibility (screening for clinically relevant depression and overt dementia by administering the BDI-II and MMSE, respectively);
- Randomization via computer-generated random numbers;
- Assignment of an individual five-digit code (XX-XXX), with the first two digits identifying the site (01: Rome, 02: Moncrivello, 03: Milan, 04: Genova, 05: Cardiff) and the last three digits deriving from the six-block randomization list;
- Dispensation of device for intervention and relative instructions;
- Dispensation of patient diary (AEs and accidental falls);
- Dispensation of logbook (adherence to intervention);
- Dispensation of actigraph and relative instructions;
- Collection of demographic and clinical data in the case report form (CRF);
- Neurological examination with EDSS score;
- Administration of BICAMS, including the SDMT, CLVT2, and BVMT-R, and SCWT;
- Administration of 2-Minute Walking Test (2MWT) in single-task and dual-task condition;
- Static posturography assessment in single-task and dual-task condition;
- Administration of questionnaires:
 - Cognitive Reserve Index questionnaires (CRQ)
 - Historical Leisure Activity questionnaire (HLAQ)
 - Temperament and Character Inventory (TCI)
 - 29-item Multiple Sclerosis Impact Scale (MSIS-29)
 - 21-item Modified Fatigue Impact Scale (MFIS-21)
 - Work Productivity and Activity Impairment: Specific Health Problems (WPAI:MS).

End of intervention period (Week 8 visit)

The following procedures will occur during the Week 8 visit:

- Return of the device;
- Check of the patient diary for AEs, including accidental falls;
- Return of the logbook;
- Double-check of the logbook and patient diary for adherence;
- Collection of data from actigraph (physical activity);
- Administration of BICAMS, including the SDMT, CLVT2, and BVMT-R, and SCWT;
- Administration of 2MWT in single-task and dual-task condition;

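### A single disclosed block size of six, completed within each centre, lets the unblinded operator who judges eligibility predict about one allocation in five with certainty

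*Protocol*

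**What the plan says.** The Randomization procedure section of the protocol gives one block size: "Randomization codes will be computer-generated in blocks of six to ensure an approximate 1:1:1 balance between the three arms". Codes are assigned "sequentially within each center as patients become eligible for randomization by an independent organization not involved in study conduction". On how blocks pass to sites it says: "Once a block is exhausted, the next available block will be allocated to a center upon the next randomization". A centre therefore finishes one block before it starts another. The section on the baseline visit repeats the block size, since part of the patient code is described as "the last three digits deriving from the six-block randomization list".

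The Blinding section describes two operators. "The treating operator at each site is not blind to intervention arm", and this person is "responsible for evaluating patient eligibility, for explaining how to use the devices and for recording and managing AEs". The assessing operator is separate and blind.

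The protocol mentions neither varied block sizes nor any withholding of the block size from sites. Under the section on informed consent and data protection, the approved protocol is distributed to the staff of all sites.

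**The concern.** Concealment depends on two things: nobody at the site can see the list, and nobody can work out its next entry. The independent organization secures the first. The second is weakened because three facts meet in one role. The block size is known and constant. A site can find its place in the block by counting its own patients. The operator who instructs patients in the devices knows which arms have been used.

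That operator also evaluates eligibility, at the same Week 0 visit at which randomization takes place. Someone who knows or suspects the next arm could bring a candidate forward, delay one, or apply a judgement-based criterion more or less strictly. The last inclusion and exclusion items on ability to comply and on interfering medical conditions leave such room. Data from screening failures are not to be analysed, so selective rejection would not show in the results.

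What is at stake is comparability of the arms at entry. The trainings are self-administered at home, so traits that are hard to measure, such as motivation, could affect outcome. The planned evaluable size is 35 per arm.

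**Working it through.** The protocol gives no predictability figure, so there is nothing to reproduce. The check works out what an observer can infer.

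**Inputs**
- Block size 6 and three arms at 1:1:1 (Randomization procedure; Participants). This implies two places per arm in each block.
- Blocks completed within centre (Randomization procedure).
- Five sites (baseline visit section). The total is 126 in the statistical plan and 132 in the synopsis; the percentages for full blocks do not depend on which is used.
- Assumption: the observer knows the block size and every earlier allocation at the site.
- Assumption: 26 patients per centre where a per-centre figure is needed. The protocol gives none; 126/5 = 25.2, rounded up.

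**Exact result for one full block.** There are 6!/(2!·2!·2!) = 90 equally likely orderings.
- Position 6 is always certain.
- Position 5 is certain when positions 5 and 6 hold the same arm: 3 × 4!/(2!·2!) = 18 orderings, and 18/90 = 1/5.
- The best guess is the arm with most places left. Its chance of being right is (largest number of places left for any arm)/(places left), averaged over the possible histories.

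| Position | Certain | At least one arm ruled out | Best guess right |
|---|---|---|---|
| 1 | 0 | 0 | 1/3 |
| 2 | 0 | 0 | 2/5 |
| 3 | 0 | 1/5 | 1/2 |
| 4 | 0 | 3/5 | 8/15 |
| 5 | 1/5 | 1 | 3/5 |
| 6 | 1 | 1 | 1 |
| Mean | 1.2/6 = 20% | 2.8/6 = 46.7% | (101/30)/6 = 56.1% |

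With unpredictable allocation the best guess is right 33.3% of the time. If all blocks are filled, 20% is 0.2 × 126 = 25.2 or 0.2 × 132 = 26.4 patients.

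**At 26 patients per centre.** This is four full blocks plus two patients in a fifth.
- Certain: 4 × 1.2/26 = 4.8/26 = 18.5%.
- Best guess right: (4 × 101/30 + 1/3 + 2/5)/26 = 14.2/26 = 54.6%.

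**With varied block sizes.** These figures come from simulation: 3,000 runs of 26 patients, with an observer who knows the set of possible sizes and all past allocations but not the size of the current block.

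| Block sizes | Certain | Best guess right |
|---|---|---|
| 6 only | 18.4% | 54.5% |
| 3 and 6 | 7.7% | 56.3% |
| 6 and 9 | 4.7% | 52.7% |
| 6, 9 and 12 | 2.3% | 51.2% |

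The simulated row for fixed sixes agrees with the hand calculation. Varying the size removes nearly all certainty but reduces successful guessing only modestly.

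**The case against.** The strongest reply is that the protocol already separates the roles. An independent organization assigns the code once a patient is eligible, and a blind assessor measures outcome. Most entry criteria are numerical limits, which restrict the scope for rejecting a candidate. The percentages also require one person to follow every allocation at a site; several operators, or unfilled blocks, would lower them.

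Much of this stands. The blind assessor limits bias in measurement, and the numerical criteria limit arbitrary rejection. They do not prevent a candidate being delayed or reordered, and a few criteria remain matters of judgement. The independent organization protects the list but not the inference from past allocations.

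Several stronger readings are tempting but not supported:
- A reader might infer that the operator controls or handles the blocks. The protocol gives assignment to the independent organization; the operator can only predict.
- A reader might infer that any resulting bias is beyond repair. Baseline SDMT, EDSS, age and other variables are recorded, so selection on measured factors can be partly adjusted for. Selection on unmeasured ones cannot.
- A reader might infer that the patient code reveals the place in the block. The text says only that three digits derive from the list, not that they encode position. Someone who sees allocations in order can count positions anyway, so the code adds little.
- A reader might infer that selection has occurred. The document shows a weakness in the design and nothing about conduct.

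**Conclusion.** The concern holds as a risk of selection bias at entry. The protocol itself fixes and discloses the scheme, so this is not a detail left to a later document.

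About one allocation in five is known in advance: 20% over full blocks, about 18% at 26 patients per centre. At least one arm can be excluded before 46.7% of allocations over full blocks. The best guess succeeds about 55–56% of the time instead of 33%.

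These figures rest on two places per arm in each block and on an operator who knows the block size and follows all allocations at the site. The 18% and 55% also assume equal recruitment across five sites. The change is worth making because it is cheap and removes nearly all certain predictions.

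**What to change.** - Have the independent organization generate blocks of randomly varying size within each centre, for example 6, 9 and 12, and keep the sizes to itself. If recruitment has begun, apply this to blocks not yet released.
- Remove the block size from documents held by sites. In the protocol it stands in the Randomization procedure section and in the patient-code item of the baseline visit section.

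At 26 patients per centre this lowers certain allocations from about 18% to about 2%. It should not be presented as making allocation unpredictable, since best-guess accuracy falls only from about 55% to 51%. If more protection is wanted, eligibility could be confirmed by someone who does not know past allocations at the site.

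The cost is a new list and a short amendment, plus somewhat looser balance at small centres. In an unfinished block of six, two arms can differ by at most 2 patients; in blocks of nine or twelve, by at most 3 or 4.

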We estimated a pre-defined 8-point non-inferiority margin, based on a significant effect of the COGNI-TRAcK in inducing an about 8-point mean increase at SDMT score (with respect to a sham intervention). Accordingly, 35 subjects per arm are required to ensure, with an approximately 85%-power level, that the lower limit of a one-side 95% confidence interval will be above the pre-defined non-inferiority margin. Therefore, considering also a drop-out rate of 25%, a total of 132 subjects should be enrolled.

Statistical methods

All analysis will be based on the intention-to-treat principle using the fully analysis dataset including all randomized patients. Missing data will be handled by multiple imputation method. Continuous data will be analyzed by parametric and non-parametric RM-ANOVAs with effect size estimation. The time-to-event data will be analyzed by Kaplan-Meier curves and Log-Rank test with a factor for treatment group.

An interim analysis will be conducted when at least 50% of the estimated sample size will complete the 8-week intervention period.

Study objectives

Primary objective	Primary endpoint
To demonstrate not inferior efficacy of exergames over COGNI-TRAcK and superior efficacy of both interventions over sham in improving sustained attention and information processing speed	Change at the SDMT from baseline to Week 8
Secondary objectives	Secondary endpoints
To demonstrate not inferior efficacy of exergames over COGNI-TRAcK and superior efficacy of both interventions over sham in improving cognitive functions	Change at the BICAMS and SCWT from baseline to Week 8
Additional objectives	Additional endpoints
To demonstrate not inferior efficacy of exergames over COGNI-TRAcK and superior efficacy of both interventions over sham in reducing the impact of MS on: - cognitive-motor interference - activities of daily living - fatigue - work productivity	Change of dual-task cost of walking and balance as estimated by the 2MWT and static posturography in dual-task vs. single-task condition from baseline to Week 8 Change at the MSIS-29 from baseline to Week 8 Change at the MFIS from baseline to Week 8 Change at the WPAI:MS from baseline to Week 8
Exploratory objectives	Exploratory endpoints
To demonstrate not inferior efficacy of exergames over COGNI-TRAcK and superior efficacy of both interventions over sham on: - physical activity - adherence	Physical activity measured by wearable actigraph Percentage of training completed at home

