Secondary endpoint: the BICAMS is recommended by an expert consensus committee of neurologists and neuropsychologists as a brief, practical and universal assessment tool for cognitive impairment in MS. The battery takes 15 minutes to complete, requires no specialist equipment and no specialist expertise in cognitive assessment. The BICAMS includes tests of mental processing speed (SDMT), verbal memory (CVLT2) and visual memory (BVRT-R). The SCWT is also included since the BICAMS does not assess some aspects of executive function. The SCWT evaluates the ability to elaborate relevant and irrelevant dimensions in parallel and to inhibit an automatic response while performing a task based on conflicting stimuli. The procedure comprised of three trials: (i) read a list of words indicating colours printed in black ink as quickly as possible; (ii) name the colour of strings of dots as quickly as possible; (iii) name the colour of the ink of words indicating conflicting colours as quickly as possible (interference condition) [30].

Additional endpoints: we estimate the magnitude of CMI by performing dual-task experiments for walking and balance. For walking, patients will be asked to perform the 2MWT in isolation without any interference (single-task condition) [36] and then to repeat the 2MWT while performing an auditory analog of the Stroop test simultaneously (dual-task cost) [37]. The difference in time spent to perform the 2MWT (dual-task *minus* single-task condition) will be calculated as dual-task cost of walking [38].

For balance, patients will be asked to maintain their balance for 30 seconds as steady as possible on a force platform recording their postural sway (static posturography) while visually focusing on a dot in front of them (single-task condition) [39]; and then to repeat the static posturography assessment while performing the SCWT [40]. The difference in postural sway (dual-task *minus* single-task condition) will be calculated as dual-task cost of balance [38].

We will minimize practice effect related to multiple assessment in two ways: (i) multiple pre-baseline testing to reduce inter-individual and intra-individual variance due to subjects not fully understanding task demands [41]; (ii) administration of alternate versions that are available for serial assessments [42].

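### The dual-task cost of walking is defined as a time difference on a test of fixed two-minute duration, so it is zero for every patient who completes both walks

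*Protocol*

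**What the plan says.** The list of baseline procedures names the test in full: "Administration of 2-Minute Walking Test (2MWT) in single-task and dual-task condition". The same test is repeated at Week 8 and Week 16.

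The Efficacy section, under additional endpoints, describes the procedure for walking. Patients first do the 2MWT alone and are asked "then to repeat the 2MWT while performing an auditory analog of the Stroop test simultaneously". It then gives the formula. "The difference in time spent to perform the 2MWT", taken as dual-task minus single-task, "will be calculated as dual-task cost of walking".

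For balance, the same section fixes the recording at 30 seconds on a force platform. The cost there is "The difference in postural sway", again dual-task minus single-task.

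The study objectives table in the synopsis lists the endpoint among the additional endpoints, assessed from baseline to Week 8: "Change of dual-task cost of walking and balance as estimated by the 2MWT and static posturography in dual-task vs. single-task condition".

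**The concern.** A test that is named for its duration does not have duration as an outcome. What can differ between two completed two-minute walks is how far the patient gets. The formula subtracts the quantity that the test holds constant.

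The wording would suit a walk over a fixed distance. There time is the outcome, and dual-task minus single-task is positive when the second task slows the patient. It does not suit the test that the protocol uses.

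Reducing cognitive-motor interference is part of the hypothesis in both the synopsis and the Study design section, and the protocol measures it in only two ways, walking and balance. If the definition were followed to the letter, the walking measure would carry no information. Analysts who noticed this later would have to redefine a protocol endpoint, possibly with data in hand.

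**Working it through.** There is no sample size, power or alpha figure to reproduce here. The check is whether the stated formula can give a usable variable.

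**Inputs**
- Duration of the walking test: 2 minutes = 120 s, from the test's name in the baseline visit procedures. The protocol does not describe the conduct of the test further.
- Conditions: the same test, alone and then with an auditory Stroop task (Efficacy section).
- Formula: cost = T(dual) - T(single), where T is time (Efficacy section).
- Endpoint: change in cost from baseline to Week 8 (study objectives table).

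**Step 1: both walks completed.** T(dual) = T(single) = 120 s, so cost = 120 - 120 = 0 s. This holds at every visit at which both walks are completed.

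**Step 2: change from baseline.** Change = 0 - 0 = 0 s, in any arm.

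**Step 3: the planned analysis.** The Statistical analysis section applies repeated measures ANOVA, with visit as the within-subject factor and arm as the between-subject factor. If the dependent variable is 0 throughout, the between-arm and residual sums of squares are both 0 and the F ratio is 0/0, which is undefined. No effect size can be computed.

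**Step 4: a walk cut short.** Suppose the patient stops at time t < 120 s.
- Stopped under dual task only: cost = t - 120 < 0. The patient who could not finish appears to have a negative cost, that is, a benefit.
- Stopped under single task only: cost = 120 - t > 0. This appears as interference, although the failure came without the second task.

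So the few non-zero values would measure non-completion, with the sign the wrong way round for the first case.

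**Step 5: comparison with balance.**

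| Measure | Fixed duration | What the protocol subtracts | Usable? |
|---|---|---|---|
| Walking | 120 s | time | No: constant when completed |
| Balance | 30 s | postural sway | Yes: measured outcome |

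Both tests have a fixed duration. For balance the protocol subtracts the measured outcome, and for walking it subtracts the duration. Nowhere does the text at hand name distance or speed as the outcome of the 2MWT, so nothing elsewhere corrects the sentence.

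**Step 6: direction under a repair.** Let D be the distance in two minutes. If the second task shortens the walk, D(dual) < D(single).
- D(dual) - D(single) < 0 when the patient is worse.
- D(single) - D(dual) > 0 when the patient is worse.
- Sway(dual) - Sway(single) > 0 when the patient is worse.

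Replacing time by distance therefore also calls for the order of subtraction to be reversed if both costs are to be positive when worse.

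**The case against.** The strongest case on the other side is that this is one wrong noun in one sentence about a third-rank endpoint. The synopsis says only that the cost is estimated by the 2MWT and does not mention time. The case report form is listed as an appendix but is not shown, and the sentence leans on cited sources that are not available here. Sites may well be recording distance already, in which case the endpoint can be restated before analysis and nothing is lost. All of that stands as a limit on the consequences. It does not rescue the sentence: the protocol is not silent on the definition but gives a formula, and the formula fails if followed. For the same reason this is not detail that a protocol may leave to the SAP.

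A reader might infer more than the document supports, in four ways.
- *The endpoint is zero for every patient, arm and visit.* This assumes that everyone completes both walks. The protocol does not say so, and an early stop gives a non-zero, though invalid, value.
- *The trial cannot answer its question on cognitive-motor interference.* The balance cost is soundly defined and remains analysable. Only the walking measure fails, and only as literally defined.
- *The two interference measures point in opposite directions.* That would follow only if someone substituted distance and kept the order of subtraction. The protocol does not do this. It is a caution for the repair, not a second error.
- *The main conclusions are at risk.* The walking cost enters no sample size or power statement, and the SDMT, BICAMS and SCWT endpoints do not depend on it.

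**Conclusion.** Wrong as written. Under the stated formula the walking cost is 0 s for every patient who completes both walks, and the change to Week 8 is 0 s in every arm for such patients. Any non-zero value comes from early stopping. The additional endpoint cannot be analysed in this form.

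The conclusion rests on one assumption: that the 2-Minute Walking Test lasts two minutes in both conditions, as its name says. Whether the needed distances are being collected cannot be judged from the protocol.

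The correction should be made, but it ranks as the repair of an additional endpoint. One of two interference measures is affected. The primary analysis, the secondary analyses, the sample size and the balance cost are untouched.

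**What to change.** Replace the sentence in the Efficacy section with a definition on the measured outcome, for example: the dual-task cost of walking is the distance covered in two minutes in the single-task condition minus the distance covered in the dual-task condition, and a positive value means a greater cost. Speed, as distance divided by 120 s, would serve equally well.

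This matches the direction of the balance cost, where dual-task minus single-task sway is already positive when worse. The balance definition needs no change. Expressing the walking cost as a percentage, 100 x (single - dual)/single, is optional: the absolute difference cures the error and keeps the form that the protocol uses for balance.

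At the same time, confirm that the case report form records distance in both conditions at all three visits and at all five sites, since a distance that was not recorded may not be recoverable. If it is recorded, the cost is one sentence in an amendment, with no added visit, procedure or patient burden. The handling of walks that are stopped early can be left to the SAP.
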